## 11.2 Collaborative Agreements Language

The agent(s) supplied by CTEP, DCTD, NCI used in this protocol is/are provided to the NCI under a Collaborative Agreement (CRADA, Agent-CRADA, CTA, CSA) between the Pharmaceutical Company(ies) (hereinafter referred to as “Collaborator(s)”) and the NCI Division of Cancer Treatment and Diagnosis. Therefore, the following obligations/guidelines, in addition to the provisions in the “Intellectual Property Option to Collaborator” (<http://ctep.cancer.gov/industry>) contained within the terms of award, apply to the use of the Agent(s) in this study:

1. Agent(s) may not be used for any purpose outside the scope of this protocol, nor can Agent(s) be transferred or licensed to any party not participating in the clinical study. Collaborator(s) data for Agent(s) are confidential and proprietary to Collaborator(s) and shall be maintained as such by the investigators. The protocol documents for studies utilizing investigational Agents contain confidential information and should not be shared or distributed without the permission of the NCI. If a copy of this protocol is requested by a patient or patient’s family member participating on the study, the individual should sign a confidentiality agreement. A suitable model agreement can be downloaded from: <http://ctep.cancer.gov>.
2. For a clinical protocol where there is an investigational Agent used in combination with (an)other investigational Agent(s), each the subject of different collaborative agreements , the access to and use of data by each Collaborator shall be as follows (data pertaining to such combination use shall hereinafter be referred to as “Multi-Party Data” .):
  - a. NCI will provide all Collaborators with prior written notice regarding the existence and nature of any agreements governing their collaboration with NIH, the design of the proposed combination protocol, and the existence of any obligations that would tend to restrict NCI's participation in the proposed combination protocol.

- b. Each Collaborator shall agree to permit use of the Multi-Party Data from the clinical trial by any other Collaborator solely to the extent necessary to allow said other Collaborator to develop, obtain regulatory approval or commercialize its own investigational Agent.
  - c. Any Collaborator having the right to use the Multi-Party Data from these trials must agree in writing prior to the commencement of the trials that it will use the Multi-Party Data solely for development, regulatory approval, and commercialization of its own investigational Agent.
3. Clinical Trial Data and Results and Raw Data developed under a Collaborative Agreement will be made available exclusively to Collaborator(s), the NCI, and the FDA, as appropriate and unless additional disclosure is required by law or court order. Additionally, all Clinical Data and Results and Raw Data will be collected, used, and disclosed consistent with all applicable federal statutes and regulations for the protection of human subjects including, if applicable, the *Standards for Privacy of Individually Identifiable Health Information* set forth in 45 CFR Part 164.
4. When a Collaborator wishes to initiate a data request, the request should first be sent to the NCI, who will then notify the appropriate investigators (Group Chair for Cooperative Group studies, or PI for other studies) of Collaborator's wish to contact them.
5. Any data provided to Collaborator(s) for Phase 3 studies must be in accordance with the guidelines and policies of the responsible Data Monitoring Committee (DMC), if there is a DMC for this clinical trial.
6. Any manuscripts reporting the results of this clinical trial must be provided to CTEP by the Group office for Cooperative Group studies or by the principal investigator for non-Cooperative Group studies for immediate delivery to Collaborator(s) for advisory review and comment prior to submission for publication. Collaborator(s) will have 30 days from the date of receipt for review. Collaborator shall have the right to request that publication be delayed for up to an additional 30 days in order to ensure that Collaborator's confidential and proprietary data, in addition to Collaborator(s)'s intellectual property rights, are protected. Copies of abstracts must be provided to CTEP for forwarding to Collaborator(s) for courtesy review as soon as possible and preferably at least three (3) days prior to submission, but in any case, prior to presentation at the meeting or publication in the proceedings. Press releases and other media presentations must also be forwarded to CTEP prior to release. Copies of any manuscript, abstract and/or press release/ media presentation should be sent to:

Regulatory Affairs Branch, CTEP, DCTD, NCI  

## 12. STATISTICAL CONSIDERATIONS

### 12.1 Study Design/Endpoints

This is a phase 2 trial in patients with measurable stage IV melanoma harboring *ERBB4* mutations treated with the tyrosine kinase inhibitor lapatinib. All patients eligible for treatment will undergo formal response evaluation after 1 and 3 cycles of therapy and every 2 cycles after that.

#### Screening

The prevalence of metastatic cutaneous melanoma patients harboring no more than two *ERBB4* mutations is 17%. If this were to apply to the screening population and if 180 patients were screened, there is an 88.9% probability of identifying at least 25 patients with an *ERBB4* mutation.

#### Treatment

The primary objective of this trial is to determine if lapatinib monotherapy is able to produce adequate numbers of clinical responses in patients with metastatic melanoma harboring *ERBB4* mutations. If so, this regimen will be considered for use in subsequent studies, to determine its role in this disease.

The study will be conducted using a phase 2 MinMax design. The objective of the trial will be to determine whether, this novel agent is able to be associated with a response rate (PR + CR) that can rule out 10% ( $p_0=0.10$ ) in favor of an improved response rate of 30% ( $p_1=0.30$ ). Using alpha=0.10 (probability of accepting a poor agent) and beta=0.10 (probability of rejecting a good agent), initially 16 evaluable patients will be enrolled in the study. If 0 to 1 of 16 patients respond (PR +CR), then no further patients will be enrolled. If 2 or more of the first 16 evaluable patients enrolled have a clinical response, then accrual will continue until a total of 25 evaluable patients have been enrolled. If 2 to 4 of the 25 have a clinical response, then this will be considered inadequate for further investigation of this regimen. If 5 or more of 25 respond, then this will warrant further investigation in a subsequent trial. Under the null hypothesis (10% response rate), the probability of early termination is 51%. If a DLT is seen in the first three patients, dose de-escalation will occur as described in section 3.3.

A variety of secondary evaluations will be performed, corresponding to the secondary

objectives listed. In all cases, the evaluations will be done with exploratory intent, and will be performed using non-parametric tests and descriptive statistics on however many samples are available. If the study terminates after only 16 patients then no further patients will be enrolled to obtain biologic endpoint data.

## **12.2 Sample Size/Accrual Rate**

The accrual ceiling will be set at 180 patients to be screened for the presence of ERBB4 mutations to allow for treatment of up to 28 patients, which would include up to 3 inevaluable patients and based on the calculation described above (Section 12.1). It is expected that 1-3 patients per month will be treated on this trial. Allowing for treatment with this agent over a two year period with follow up, it is expected that the trial will be completed in approximately 3-5 years.

## **12.3 Stratification Factors**

N/A

## **12.4 Analysis of Secondary Endpoints**

Progression-free survival will be calculated using the Kaplan-Meier method.

Toxicity data will be obtained, and if there are 5 or more patients who experience Grade 3 or greater toxicity attributable to the agent, then comparisons between this cohort and patients who tolerated the same course of lapatinib without toxicity across grades of toxicity with respect to outcome (response) and clinicopathological parameters (age, sex, type of visceral involvement) may be done using a Kruskal-Wallis test. Otherwise, toxicities will be tabulated and described.

The association of response to lapatinib (PR as defined by RECIST) and presence of concomitant activating oncogene mutations or loss of tumor suppressor function will be examined in a Fischer's exact test.

Comparisons between the pERBB4 : total ERBB4 and phospho Akt : total Akt ratio will be made by subtracting pre-treatment from posttreatment levels and determining the statistical significance of the difference using a Fischer's exact test. Similarly, pErk and pSTAT levels will be evaluated for a change from baseline levels. These measures will all be evaluated with exploratory intent, and findings will be reported without formal adjustment for multiple comparisons, but in the context of a study with multiple exploratory analyses performed.

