### 1.2. Secondary Objectives

- To determine the progression free survival of patients with stage IV melanoma treated with lapatinib monotherapy.
- To evaluate the safety of lapatinib in patients with metastatic melanoma
- To determine the impact of additional genetic alterations on the response to lapatinib in melanoma harboring *ERBB4* mutations
- To develop a clinically applicable biomarker predictive of response to lapatinib in melanoma harboring *ERBB4* mutations
- To determine the pharmacokinetics of lapatinib administered as 500 mg orally twice daily on a continuous schedule in patients with metastatic melanoma harboring *ERBB4* mutations

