## 2.4 Correlative Studies Background

### Genetic Fingerprinting of Melanoma Samples

Response to lapatinib in patients with metastatic melanoma harboring *ERBB4* mutations is determined by

- (1) the intrinsic type of the individual *ERBB4* mutation and its impact on receptor activation via mechanisms like increased ligand binding, increased receptor dimerization, increased ATP binding, and increased transphosphorylation of the paired receptor, and
- (2) extrinsically, by other genetic alterations of the tumor and their influence on aberrant cell signaling.

With respect to activating somatic mutations of the ERBB4 receptor, major oncogenic events in melanoma like activation of the MAPK kinase pathway through activating mutations in the BRAF kinase (present in more than 60% of melanomas), activation of the PI3K-Akt pathway through PTEN loss (20 – 50% of melanomas), or increased cell cycle progression via loss of the INK4A (p16) locus do not occur in an exclusive fashion and might therefore facilitate the activation of escape pathways following Erbb4 inhibition with lapatinib.

Therefore, knowledge of other major genetic alterations in these melanoma samples will aid in

1. Identifying tumors less responsive and/or resistant to lapatinib treatment
2. The design of combination molecular therapy by targeting escape pathways, as the majority of these pathways are now amenable to pharmacological manipulation

In addition to all 28 exons of ERBB4 (please see Appendix B for ERBB4 primers), exons of most common oncogenes / tumor suppressor genes affected most frequently by genetic alterations in cutaneous melanoma will be analyzed by Sanger sequencing (please see Section 5.4 and Appendices H-J).

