##### 5.4.2.4.2 *Genetic markers predicting response to lapatinib in melanoma harboring activating ERBB4 mutations*

Genomic DNA extracted from patients tissues and used for ERBB4 mutation analysis will be sequenced for the presence of concomitant oncogene mutations in the RAF / RAS family and the tumor suppressor genes INK4/p16 and TP53 as outlined in section 5.4.2.4.1 above. The association of response to lapatinib (PR as defined by RECIST) and presence of concomitant activating oncogene mutations or loss of tumor suppressor function will be examined in a Fisher's exact test design:

	PR, CR – response to lapatinib	PD – progression of disease
Presence of mutation		
Wild type – no concomitant mutation		

Validation of any statistically significant association will require a larger follow-up study.

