**Target lesions.** All measurable lesions up to a maximum of 2 lesions per organ and 5 lesions in total, representative of all involved organs, should be identified as **target lesions** and recorded and measured at baseline. Target lesions should be selected on the basis of their size (lesions with the longest diameter), be representative of all involved organs, but in addition should be those that lend themselves to reproducible repeated measurements. It may be the case that, on occasion, the largest lesion does not lend itself to reproducible measurement in which circumstance the next largest lesion which can be measured reproducibly should be selected. A sum of the diameters (longest for non-nodal lesions, short axis for nodal lesions) for all target lesions will be calculated and reported as the baseline sum diameters. If lymph nodes are to be included in the sum, then only the short axis is added into the sum. The baseline sum diameters will be used as reference to further characterize any objective tumor regression in the measurable dimension of the disease.

**Non-target lesions.** All other lesions (or sites of disease) including any measurable lesions over and above the 5 target lesions should be identified as **non-target lesions** and should also be recorded at baseline. Measurements of these lesions are not required, but the presence, absence, or in rare cases unequivocal progression of each should be noted throughout follow-up.

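### The genetic-alteration objective is tested only by Fisher's exact test on RECIST response, which cannot reach 5% if the trial stops at 16 patients and leaves recorded tumour-size change unused

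*Combined protocol and SAP*

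**What the plan says.** Section 1.2 lists the objective: "To determine the impact of additional genetic alterations on the response to lapatinib in melanoma harboring" ERBB4 mutations. Section 2.4 gives one purpose of the genetic work as "Identifying tumors less responsive and/or resistant to lapatinib treatment".

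For the analysis, Section 12.4 states that the association of RECIST response with "presence of concomitant activating oncogene mutations or loss of tumor suppressor function will be examined in a Fischer's exact test". Section 5.4.2.4.2 says the same association "will be examined in a Fisher's exact test design", with a table whose columns are "PR, CR – response to lapatinib" and progression. Stable disease has no column.

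On the measurements, Section 10.1.2 states: "The baseline sum diameters will be used as reference to further characterize any objective tumor regression in the measurable dimension of the disease". Section 10.1.4.1 defines partial response as at least a 30% fall from that sum, and the Section 9 calendar repeats tumour measurements at each restaging. No planned analysis uses the size change itself.

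On numbers, Section 12.1 says that after a positive first stage "accrual will continue until a total of 25 evaluable patients have been enrolled". It also says: "If the study terminates after only 16 patients then no further patients will be enrolled to obtain biologic endpoint data". The same section calls all secondary evaluations exploratory, using non-parametric tests and descriptive statistics. No alpha, effect size or power is given for the genetic test.

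**The concern.** Whether an alteration makes a tumour less responsive is a question of degree. The plan answers it with a two-category outcome in at most about 25 patients. At the 30% target rate that means 7 or 8 responders (0.30 × 25 = 7.5); after a first-stage stop it means none or one. The graded measurement is collected anyway.

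What is at stake is the yield of a listed secondary objective. In one of the two outcomes that the design provides for, the planned test has no chance of showing anything at the usual level.

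**Working it through.** **1. The plan's own figure.** Probability of stopping, 0 or 1 responders of 16:
- at 10% response: 0.9^16 + 16 × 0.1 × 0.9^15 = 0.185 + 0.329 = 0.515, which matches the stated 51%;
- at 30% response: 0.7^16 + 16 × 0.3 × 0.7^15 = 0.003 + 0.023 = 0.026.

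**2. Fisher's test after a stop.** With no responder, p = 1. With one responder, in a group of size a out of 16, that table has probability a/16. If a is below 8 the two-sided p is a/16; otherwise it is 1. The minimum is at a = 1: p = 1/16 = 0.0625. A group of 5 gives 5/16 = 0.3125, and groups of 8 and 8 give 1. The printed table drops stable disease, so its n is 16 or fewer and its minimum, 1/n, is no smaller.

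A simulation conditional on 0 or 1 responders (groups of 10 and 6; 10% response and 60% progression, both assumed) gave the rank test on size change about 18% power at 0.8 SD, 25% at 1.0 and 51% at 1.5. Fisher's test had 0% throughout.

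**3. Full accrual, 25 patients.** Inputs:
- N = 25 and response 30%, from Section 12.1.
- Groups of 16 mutated and 9 wild type, a BRAF-only comparison. In Table 4, 7 of the 11 ERBB4-mutant samples carry BRAF V600 changes, and 25 × 7/11 = 15.9.
- Assumed, not in the documents: 40% progression, two-sided 5%, size change normal with shift d SD in the mutated group, and half of progressors tied at the worst rank.

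The response cut c solves [16Φ(c − d) + 9Φ(c)]/25 = 0.30; the progression cut is set likewise at 0.60. At d = 1.0, response is 17% mutated and 52% wild type: (16 × 0.174 + 9 × 0.524)/25 = 0.300.

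Power in % (20,000 simulated trials per row; simulation error at most about 0.35 points per entry; rank test by its large-sample form):

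| d | Printed table, Fisher | Printed table, mid-p | Responder vs not, Fisher | Rank test | Rank minus printed Fisher | Rank minus printed mid-p | Rank minus responder vs not |
|---|---|---|---|---|---|---|---|
| 0 | 2.6 | 4.2 | 2.6 | 4.6 | | | |
| 0.5 | 12.2 | 16.8 | 10.3 | 17.8 | 5.6 | 1.0 | 7.5 |
| 0.8 | 28.5 | 35.8 | 23.0 | 38.9 | 10.4 | 3.1 | 15.9 |
| 1.0 | 43.2 | 51.3 | 34.5 | 54.6 | 11.4 | 3.3 | 20.1 |
| 1.2 | 59.2 | 67.0 | 48.2 | 71.2 | 12.0 | 4.2 | 23.0 |
| 1.5 | 79.9 | 85.0 | 67.9 | 88.4 | 8.5 | 3.4 | 20.5 |

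The mid-p column removes most of Fisher's conservatism on the same table. What remains, 1 to 4 points, is due to the outcome scale.

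**4. Sensitivity.**
- *10% response, 60% progression* (25 patients, ignoring the stage-one stop): the gain over the printed table is 32.7 − 16.7 = 16.0 points at 0.8 SD and 47.6 − 26.1 = 21.5 at 1.0 SD.
- *Heavy tails* (t, 3 df), 30% response, 1.0 SD: 32.3 printed, 25.9 responder versus not, 40.5 rank; gains 8.2 and 14.6.
- *Two wild-type patients, no worst-rank ties, 0.5 to 1.0 SD:* the rank test has only 5 to 16% power, between about 2 points below and 7 above responder versus not. The printed table has 0 to 9%.
- *All-or-none effect*, response 19% versus 50%: 17.5 printed, 28.4 responder versus not, 24.4 rank. At 10% versus 60%: 49.9, 68.9 and 54.4. The rank test gains 4.5 to 6.9 points over the printed table but loses 4.0 to 14.5 to responder versus not.

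**The case against.** The strongest case against is that the plan makes no error here. The objective is worded as response, RECIST response is the trial's clinical currency, and it requires confirmation, which best percent change does not. All secondary evaluations are exploratory, Section 12.1's mention of non-parametric tests leaves room for a rank test, and Section 5.4.2.4.2 says any significant association needs a larger follow-up study. All of this stands, and it limits the point to an added analysis.

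The split also matters. The printed comparison row is patients with no concomitant mutation, yet all 11 ERBB4-mutant samples in Table 4 carry a BRAF or NRAS mutation. A pooled any-mutation comparison may have almost no wild-type patients, and no outcome scale repairs that. The 16/9 split fits a single-gene BRAF comparison only.

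A reader might infer three stronger things:
- *That dichotomising alone costs 10 or 20 points.* Against the table the protocol prints, it costs about 1 to 4; the rest of that gap is Fisher's discreteness. The larger figures belong to a responder-versus-non-responder table that Section 5.4.2.4.2 does not print.
- *That a real effect would be reported as absent.* Nothing in the documents says a non-significant result will be read that way.
- *That the choice of combination therapy rests on this test.* Section 2.4 says only that the genetic knowledge will help.

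**Conclusion.** The point holds as a low-severity improvement. Its firmest part needs no effect-size assumption: after a first-stage stop the planned test cannot reach two-sided 5%. The 51% chance of that stop applies at a true 10% response rate; at 30% it is 2.6%.

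At 25 patients the direction is clear for a graded effect in reasonably balanced groups, but the size is conditional. Under the stated assumptions the rank test gains about 6 points at 0.5 SD and 9 to 12 at 0.8 to 1.5 SD over the printed table, and about 8 to 23 over responder versus non-responder. Gains grow at lower response rates, shrink with heavy tails, are of little use when almost no patients are wild type, and turn negative against responder versus non-responder for a purely all-or-none effect. None of these is a document figure, and they should be quoted only with their assumptions.

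**What to change.** In Sections 12.4 and 5.4.2.4.2, add for each alteration a two-sided exact Wilcoxon rank-sum test on best percent change from baseline in the target-lesion sum, up to progression. Report the Hodges-Lehmann difference with its 95% interval. Where the estimate or a limit depends on a worst-ranked patient, report it as not estimable.

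Give the worst tied rank to patients with no evaluable reduction before progression by new or non-target lesions, symptomatic deterioration, early death or unknown status. This agrees with Section 12.5.2, which counts categories 4 to 9 as treatment failure.

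Keep the RECIST table with Fisher's test beside it as the clinical display; it also covers an all-or-none effect.

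Cost: about three sentences and minor programming, with no new scans, data or patients. The downside is that percent change is unconfirmed and less directly clinical than RECIST response.

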##### **5.4.2.1 *Timing of biopsy***

Biopsies will be performed at the following times:

- After consent, prior to treatment with lapatinib
- At day 14 of cycle 1 (+/-5 days)
- At day 28 of cycle 3 (+/-5 days)

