#### 5.4.2.4 *Studies*

Snap-frozen core-needle biopsies obtained from patients pre- and post treatment with lapatinib will be utilized to make cell lysates for the analysis of the changes in protein levels and phosphorylation status of the ERBB4 and Akt pathways:

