#### 5.4.2.4.3 *Correlative Protein Expression Studies*

Tissue obtained at follow-up biopsies (outlined below) will be collected, stored, and in the future analyzed by quantitative Western Blotting for phosphoprotein expression of pERBB4, pAKT, and pERK. Phospho- and total protein expressions will be compared to baseline levels, and changes will be correlated using the Fischer's exact test design for response to lapatinib. The development and translation into clinically applicable IHC testing will need to await larger studies.

**Immunoprecipitation and protein blotting.** Melanoma tissue from core needle biopsies will be gently washed three times in PBS and then lysed using 0.5–1.0 mL 1% NP-40 lysis buffer (1% Nonidet P-40, 50 mM Tris-HCl pH 7.5, 150 mM NaCl, 1× EDTA-free Complete Protease Inhibitor tablet (Roche), 1 µM sodium orthovanadate, 1 mM sodium fluoride and 0.1% β-mercaptoethanol) for 20 min on ice. Extracts are centrifuged for 10 min at 20,000g at 4 °C. Five hundred microliters of supernatant will be immunoprecipitated overnight using 20 µL of anti-ERBB4-conjugated agarose beads (Santa Cruz Biotechnology). The immunoprecipitates will be washed and subject to SDS-PAGE and protein blotting. Primary antibodies used in our analysis are anti-ERBB4 (Santa Cruz Biotechnology), anti-P-ERBB4(Y1162) (Abgent), anti-P-ERBB4(Y1284) (Cell Signaling), anti-PY20 (Zymed-Invitrogen), anti-P-ERK1/2 (T202/Y204), anti-ERK1/2, anti-P-AKT (S473), anti-AKT (Cell Signaling), and anti-α-tubulin (Calbiochem-EMD Biosciences).

**Immunoblot quantification analysis.** Scanned films from protein blot analysis of SDS-PAGE will be analyzed using ImageJ (National Institutes of Health, Bethesda, Maryland, USA). Individual bands will be quantified and plots generated to determine the intensities in each band. The data are exported to Microsoft Excel and analyzed further for the ratio of phosphoprotein to total protein.

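### Section 12.4 names Fisher's exact test for a paired change in a continuous protein ratio, which it cannot assess, and the mutation table in 5.4.2.4.2 gives stable disease no place

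*Combined protocol and SAP*

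**What the plan says.** **Protein changes.** Section 5.4.2.4 plans lysates from biopsies taken before and after treatment, for "analysis of the changes in protein levels and phosphorylation status of the ERBB4 and Akt pathways". In 5.4.2.4.3, bands are quantified by densitometry and the data are "analyzed further for the ratio of phosphoprotein to total protein". Section 12.4 then compares the pERBB4:ERBB4 and pAkt:Akt ratios, the comparison being "made by subtracting pre-treatment from posttreatment levels and determining the statistical significance of the difference using a Fischer's exact test".

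Section 5.4.2.4.3 puts the same test to another use: "changes will be correlated using the Fischer's exact test design for response to lapatinib". Neither section gives a cut-point, or says whether these are one analysis or two.

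Section 5.4.2.1 schedules two on-treatment biopsies, at cycle 1 day 14 and cycle 3 day 28, each within 5 days. Section 12.4 does not say which one is the post-treatment value. Section 5.4.2.4.3 lists "phosphoprotein expression of pERBB4, pAKT, and pERK", while 12.4 adds that "pErk and pSTAT levels will be evaluated for a change from baseline levels". No STAT measurement or antibody appears in 5.4.2.4.3.

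**Mutations and response.** Section 5.4.2.4.2 plans a Fisher table of concomitant mutation (present or wild type) against outcome. Its two outcome columns are PR with CR, and PD. The sentence introducing the table, and its counterpart in 12.4, give response as PR only. The primary endpoint in 12.1 is PR + CR. Section 12.5.2 lists SD as category 3 and counts categories 4 to 9 as treatment failure.

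**Status.** Section 12.1 makes all secondary evaluations exploratory, using non-parametric tests and descriptive statistics. Section 12.4 makes no multiplicity adjustment, and 5.4.2.4.2 asks for validation of any significant association in a larger study.

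**The concern.** Fisher's exact test compares proportions between independent groups in a table of counts. A post-minus-pre ratio is one continuous number per patient, so the sentence in 12.4 cannot be carried out as written. Whoever runs the analysis must supply another test, or a dichotomy that the plan does not define, and must also choose the biopsy and the scale. Section 5.4.2 makes biopsies optional and limits them to the coordinating center, so the data set may be small and sensitive to those choices.

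In the mutation table, an SD patient can be left out, counted with non-response or counted with progression. These codings answer different questions and can give different results. Biomarker development and the effect of additional genetic alterations are listed secondary objectives (1.2), so both analyses are likely to be reported.

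**Working it through.** **Inputs.** The named tests, table columns, response categories and visit windows come from 12.4, 5.4.2.4.2, 5.4.2.4.3, 12.5.2, 5.4.2.1 and 5.3.3. The documents give no number of pairs, effect size, variability, mutation counts, alpha or sidedness for these analyses; such values below are assumptions. The plan offers no figure of its own here to reproduce.

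**1. Can a Fisher table be built for 12.4?** Only by adding something that the plan does not state.
- *High/low before against high/low after.* The two rows are the same patients, so independence fails. Example: 16 pairs, 12 high before and 6 high after, all 6 changes in one direction. Fisher's test on the rows as if independent gives p = 0.073. The exact paired (McNemar) test gives 2 × 0.5^6 = 0.031.
- *Fall/rise against response.* This is the 5.4.2.4.3 question. If the ratio falls in all of 10 patients, one column is empty and p = 1.0. The table then carries no information on whether the ratio changed, because it was not built to.

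**2. What a paired rank test can show.** The smallest two-sided exact signed-rank p is 2/2^n: 0.125 for n = 4, 0.0625 for n = 5, 0.031 for n = 6 and 0.008 for n = 8.

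Simulated power at two-sided 0.05 (40,000 runs; assumed log-scale shift −0.7, about a halving; between-patient SD 1, measurement SD 0.5):

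| Pairs | Log ratio | Raw difference |
|---|---|---|
| 6 | 0.35 | 0.35 |
| 8 | 0.60 | 0.52 |
| 10 | 0.78 | 0.68 |

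**3. Change by response, if wanted.** The smallest two-sided rank-sum p is 2/C(a+b, a): 2/28 = 0.071 for 2 against 6 patients, 2/45 = 0.044 for 2 against 8, and 2/56 = 0.036 for 3 against 5.

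**4. Biopsy timing.** The latest in-window cycle 1 biopsy is day 14 + 5 = 19. The earliest scheduled scan is day 28 − 5 = 23.

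**5. Stable disease in the mutation table.** Assume 5 responders (1 mutated), 10 PD patients (7 mutated) and 10 SD patients. With N patients and M mutated, P(x) = C(M,x)·C(N−M,5−x)/C(N,5), where x is the number of mutated responders. The two-sided p sums every P(x) no larger than P(1). C(15,5) = 3003 and C(25,5) = 53130.

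| Handling of SD | Mutated: responders vs comparator | Sum | p |
|---|---|---|---|
| Left out | 1/5 vs 7/10 | (21+280+56)/3003 | 0.119 |
| Kept, 10 mutated | 1/5 vs 17/20 | (21+630)/53130 | 0.012 |
| Kept, 8 mutated | 1/5 vs 15/20 | (126+2016)/53130 | 0.040 |
| Kept, 5 mutated | 1/5 vs 12/20 | (792+6435+1287)/53130 | 0.160 |
| Kept, 1 mutated | 1/5 vs 8/20 | (53130−20160)/53130 | 0.621 |
| Kept, 0 mutated | 1/5 vs 7/20 | 53130/53130 | 1.0 |

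With 9 of 10 PD patients mutated instead, leaving SD out gives (1+50)/3003 = 0.017. Keeping 10 SD patients, 5 of them mutated, gives (252+3150+3003)/53130 = 0.121. Leaving SD out can therefore raise or lower p.

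**The case against.** The strongest defense is that little rides on this. The analyses are exploratory and unadjusted, and 12.1 already points to non-parametric methods. That limits the severity, but a general line does not replace a test named for a specific comparison. It does show that a signed-rank test fits the plan's own approach.

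A reader might infer that the method will inevitably be picked after the results are known. The documents do not support that: 5.4.2.4.3 stores the follow-up tissue for later analysis, so the test and time point can still be fixed before any blot is read.

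A reader might also infer that complete responders would be excluded from the mutation analysis. The heading of the table in 5.4.2.4.2 includes CR, so the PR-only wording is best read as a slip.

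Response against progression is a legitimate contrast, since 2.4 seeks tumors that resist lapatinib. Nor does leaving out SD generally inflate false positives. Take 25 patients, a marker with no effect on response and 50% prevalence, and true response rates of 10/20/30%. Rejection at 0.05 is 1.3/2.9/3.5% when SD makes up 50% of non-responders in one marker group and 30% in the other. It reaches 5.8/10.7/12.3% only with a split as extreme as 70% against 10%. What stands is that the plan does not say which contrast is meant, or where SD patients go.

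**Conclusion.** Minor, and wrong as written. The test named in 12.4 cannot assess the within-patient change it is assigned to; that follows from the text and needs no assumption. SD is unplaced in the mutation table, and 12.5.2 does not settle it because SD is category 3 and only categories 4 to 9 are mapped to failure. The p-value shifts rest on assumed counts: they show that the coding can matter in either direction, not that it will. The power advantage of the log scale likewise rests on assumed variability and is absent at 6 pairs.

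Two stronger readings should be avoided. Six pairs is not a required minimum, because the plan sets no alpha or sidedness here: at two-sided 0.10, or in a one-sided 0.05 test for a fall (1/2^5 = 0.031), 5 pairs could suffice. And the day 14 biopsy precedes only the first *scheduled* scan. The note in 5.3.5 and the study calendar in section 9 allow earlier assessment when clinically indicated, and 10.1.1 provides for progression before the end of cycle 1.

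The primary response decision is untouched.

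**What to change.** **Section 12.4, protein ratios.** Replace Fisher's test with an exact Wilcoxon signed-rank test on the paired change, preferably in log ratio, with a stated rule for undetectable bands. Name one post-treatment biopsy as the main time point before any blot is read, and treat the other as descriptive; cycle 1 day 14 is a reasonable choice. Report the median change and range at any sample size, and note the limit on the attainable p-value when there are 5 or fewer pairs.

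**Sections 12.4 and 5.4.2.4.3.** State whether change by response is also intended. If so, label it as a separate question and use a rank-sum test, or Fisher's test with a stated cut-point. Make the protein lists agree on pSTAT.

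**Sections 5.4.2.4.2 and 12.4, mutations.** Change PR to CR+PR in the text. Make the main table CR+PR against all other patients in the response analysis set used for the primary endpoint, and keep Fisher's exact test. That set needs one definition, since 12.1 and 10.1.1 count evaluable patients and 12.5.2 all eligible patients. If response against progression is wanted, show it as a separately labelled table.

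**Cost.** Wording in three sections. One biopsy time point goes without a test. Counting SD and unassessable patients as non-response may misclassify a few, and loses power if SD patients carry the mutation less often than PD patients.
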